24.4.5 Diagnosis and Symptom onset Start Dates

Missing start dates for diagnosis and symptom onset will be imputed according to the following rules:

• If Day is missing (DD): The first day of the month will be used, i.e., 01

• If Month is missing (MMM): January will be used, i.e., 01

If both dates are missing hence 01-01 should be used. After imputation, the calculation of both 'time-since-diagnosis' and 'time-since-symptom-onset' should be done in relation to treatment start date (i.e., TRTSDT – DIAGDTC, TRTSDT – SYMPDTC), meaning that if the diagnosis was done within the same year of treatment start, then time-since-diagnosis should be <1.

24.5 Data with Multiple Records

24.5.1 Dose Changes in Medication

Dose changes in medications are recorded on multiple rows in the dataset, with different start and stop dates. When classifying medications into periods (prior to IMP, continued after first dose of IMP, started at or after first dose of IMP), each dose is considered a separate medication, and the same medication can be assigned to several periods for the same patient. Within a period, multiple entries contribute as a single count.

24.5.2 Changes in Intensity or Seriousness of Adverse Events

Changes in adverse event intensity or seriousness are recorded on multiple rows in the dataset. An adverse event that changes in intensity or seriousness will contribute to the count of events as a single event.

In summaries of adverse events presented by intensity, the maximum intensity of the adverse event will be used. The maximum intensity is searched for in events with changes, as well as over repeated events based on the preferred term. For TEAEs and causally related TEAEs, the record(s) with the maximum intensity and maximum related intensity within an analysis phase will be flagged in ADaM data with ASEVMAX=Y and ARSEVMAX=Y, respectively. Adverse events for which information on intensity is missing will be classified as *severe*. Adverse events for which information on seriousness is missing will be classified as *serious*.

During the course of an event, information about all changes in intensity are collected (intensity and start date of intensity change). In ADaM data, changes in intensity are included as additional records (rows) to the originally reported adverse event reflecting the way data are collected. For instance, an adverse event that changes from mild to moderate will have two records, one with intensity mild and one with intensity moderate. Start date for the first intensity will be the start date for the originally reported event. The stop date for the last intensity will be the stop date for the originally reported event, and for the preceding intensities the stop date will be set to the date of reported change in intensity minus 1, or the date of reported change if a change occurring on the same day as the originally reported event, or if there is more than one change on a day.

If an adverse event changes from non-serious to serious, in addition to the originally reported adverse event start date, the start date for the seriousness is reported. However, the event is only reported as serious in the adverse event eCRF. In ADaM data, adverse events that change

from non-serious to serious will be included as two records, one with seriousness non-serious and one with seriousness serious. The start date for the non-serious event will be the start date for the originally reported adverse event, and the stop date will be set to the start date of the seriousness minus 1. The stop date for the serious event will be the stop date for the originally reported adverse event. If an intensity and seriousness is reported on the same date, record will be added reflecting both the change in intensity and seriousness (e.g. for an adverse event originally reported as being mild and non-serious is reported as having changed to severe and serious on the same date, there will be one additional record in data).

Duration (days) will be calculated for each intensity/seriousness based on the intensity/seriousness start-and stop dates. No duration will be calculated for adverse events with incomplete or missing start-or stop date, or for events ongoing at the end of the study.

24.6 Handling Exposure Data

Exposure across the whole study period will be assigned PARAM = 'Study' and exposure within visit intervals will be assigned PARAM = 'V1_V2', PARAM = 'V2_V3', and PARAM = 'V3_V4', etc., for intervals between V1 and V2, V2 and V3, V3 and V4, etc., respectively.

Exposure to dose of Lu AF82422 in the study period is calculated as:

(Date of last dose +28) – (Date of first dose +1)

Exposure in days will be given in variables EXP1D, EXP2D, EXP3D. Corresponding exposure in years will be given in variables EXP1Y, EXP2Y, EXP3Y derived as exposure in days divided by 365.25.

The average dose in the full study period will be derived.

For the study time-interval the duration of exposure to dose will be categorized into the intervals 1-7 days, 8-14 days, ..., etc.

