- Patients who enter the OLE will receive the first open-label dose (Visit 1E) on the same day as the EoTDBP or as soon as possible thereafter, but no later than 5 months after the EoTDBP Visit and will be enrolled to OLE no later than the end of Q1 2024.
- In the OLE, patients will receive Lu AF82422 until Visit 24E (Week 92E) and complete the EoTOLE at Visit 25E (Week 96E). Visit 13E should occur at Week 48E, 4 weeks after Visit 12E. However, in the exceptional cases where sites have not yet received Institutional Review Board/Ethics Committee approval for Protocol Edition 6.0, Visit 13E can be delayed until approval is in place but no later than 5 months after Visit 12E.
- Patients who withdraw, except for those who withdraw their consent, will be scheduled for a Withdrawal Visit to undergo clinical and safety assessments as soon as possible.
- All patients (except the ones withdrawing consent) will be scheduled for a Safety Follow-up Visit 20 weeks after their last IMP dose, regardless if they received their last dose in the DBP or OLE, or if they withdrew.
- Patients will be monitored after IMP administration for immediate drug reactions for a minimum of 2 hours with vital signs taken every 30 minutes ±5 minutes from the end of the saline flush or until stable, whichever is later (only applicable through Visit 12E). Beginning at Visit 13E, blood pressure and pulse will only be measured immediately prior to and immediately after IMP administration, inclusive of the saline flush (±5 minutes).
- CSF assessments for evaluation of pharmacokinetics (PK), TE, and biomarkers at baseline and after initiation of treatment will be collected according to Panel 2. CSF sampling is not applicable for patients with contraindications of lumbar puncture, history of severe post-lumbar puncture headache, on-going skin infection at the lumbar puncture injection site, or documented history of vertebral deformities, major lumbar

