3.2 Definition of Periods

The study consists of the following periods:

- Screening Period (4 weeks): Screening Visit (V1) to Randomization Visit (V2)
- Randomization Period (2 weeks): Randomization Visit (V2) to Baseline DB Visit (V3)
- Double-blind Treatment Period (varying: 48 to 72 weeks): Baseline DB Visit (V3) to EoTDB Visit (V24) – Time point to be defined by IMP initiation on V3
- Optional Open-Label Treatment Period (48 weeks): from Baseline OLE Visit (V1E) to EoTOLE (V13E) - Time point to be defined by IMP initiation on V1E

Patients will subsequently after end IMP administration enter:

- Safety Follow-up Period 1 following DB (20 weeks): following the EoTDBP Visit (V24) to Safety Follow-up Visit (V25)
- Safety Follow-up Period 2 following OLE (20 weeks): following the EoTOLE Visit (V13E) to Safety Follow-up Visit (SFU-E)

Due to the late approval of the OLE protocol amendment some participants entering the OLE might have entered the first safety follow-up period prior to entering the OLE, and hence would have two safety follow-up periods.

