In addition, concomitant medications continued or started after first dose of IMP will classified into two overall groups depending on purpose, i.e., treatment of motor symptoms ('anti-Parkinson medication') and treatment of autonomic dysfunction ('Autonomic dysfunction medication'). The classification will be done prior to unblinding according to Protocol Appendix VII.

The tables will be based on the APTS.

10 Exposure

For each infusion visit, information related to infusion completed as planned (yes/no), infusion temporarily interrupted (yes/no), and infusion lasted longer than 30 (+10) minutes (yes/no), as well as descriptive statistics for the duration of infusions (this duration includes duration of any infusion interruptions) and duration of temporary interruptions will be summarized by treatment group for the DB-Period and the OLE-Period, respectively.

Patients, who at any point during the study received a different dose than what was planned, will be listed for each period. The listing will include date of infusion visit, planned dose for the patient and actual dose received for the patient.

Exposure (days) to IMP will be calculated as:

(Date of last dose + 28 days) – Date of first dose + 1

Exposure to IMP will be summarized in weeks using descriptive statistics.

Study 18331A - Statistical Analysis Plan

Patient years of exposure (PYE) will be calculated as the sum of the number of days of exposure to IMP for each patient, divided by 365.25 days.

The number and percentage of patients with different durations of exposure (≤ 4 weeks, >4 to ≤ 8 weeks, >8 to ≤ 12 weeks, ..., >68 to ≤ 72 weeks) will be presented.

Exposure will be summarized based on the APTS. In addition, all infusion data will be listed.

11 Fall Diary Compliance

The Fall Diary is planned to be dispensed and filled out in 5 periods during the study, i.e., at a two-week Baseline period and at four post-baseline four-week periods, respectively. For each period, days where the fall diary has been missed will be summarized and presented by period and treatment group. Furthermore, the number of patients missing 7 days or more (at Baseline and at subsequent periods) and 14 days or more (at subsequent periods) in each period will be presented by period and treatment group.

A day where the fall diary has been missed is defined as a day where the subject did not fill out anything in the diary.

The summaries will be based on the FAS.

12 Wearable Compliance

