16.1.5 Presentation of Adverse Events

All adverse events will be listed for the APRS.

An overview of the PYE and number and percentage of patients with TEAEs, serious adverse events (SAEs), or adverse events leading to withdrawal, and of patients who died will be provided based on the APTS for the open-label and safety follow-up period.

For TEAEs, SAEs, and adverse events leading to withdrawal/death, the total number of events will be included.

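### Whole-study exposure in SAP 24.6 runs from first to last dose with no deduction for permitted dose-free intervals, and the SAP does not say which exposure value feeds patient-years

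*SAP*

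**What the plan says.** SAP 24.6 sets up a whole-study value: "Exposure across the whole study period will be assigned PARAM = 'Study". The rule is introduced with the words "Exposure to dose of Lu AF82422 in the study period is calculated as", and the formula given there, outer brackets aside, is "Date of last dose +28) – (Date of first dose +1"; the result is also converted to years. SAP section 10 (Exposure) gives "Date of last dose + 28 days) – Date of first dose + 1", again without the outer bracket, and continues: "Patient years of exposure (PYE) will be calculated as the sum of the number of days of exposure to IMP for each patient". That total is then turned into years using 365.25 days per year. The adverse-event summary in SAP 16.1.5 opens with "An overview of the PYE and number and percentage of patients with TEAEs".

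Two dose-free intervals are permitted. The synopsis and Protocol 4.1 allow the first open-label dose on the day of the DBP end-of-treatment visit or up to 5 months later. Because the OLE amendment was approved late, SAP 3.2 foresees that "some participants entering the OLE might have entered the first safety follow-up period prior to entering the OLE". For sites still awaiting approval of Edition 6.0, the synopsis adds that "Visit 13E can be delayed until approval is in place but no later than 5 months after Visit 12E".

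Other text points to calculation by period. Protocol 17.8 summarizes exposure separately for each period. SAP section 5 bases exposure outputs on the treated set in the DBP and on the OLE set in the extension. The duration categories in SAP section 10 stop at 72 weeks, the longest DBP.

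**The concern.** A first-to-last-dose formula equals time on a 4-weekly schedule only if no dose interval exceeds 28 days. The protocol plans for two that may. The DBP end-of-treatment visit already falls about 4 weeks after the last double-blind dose, so the 28 days credited to that dose are used up before the Visit 1E gap begins. All of that gap is then counted as exposure. The Visit 13E gap lies inside the OLE, so splitting exposure by period does not remove it.

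Protocol 4.2 gives long-term safety as one purpose of the OLE, and PYE is the SAP's summary of how much experience supports it. As written, two programmers could produce materially different PYE from the same infusion records. Any event rate per patient-year built later on the inflated value would be too low relative to dosed time.

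**Working it through.** The documents state no exposure total, so there is no figure to reproduce. The schedule inputs can be checked: 4 + 2 + DBP + OLE + 16 weeks gives 70 to 94 weeks without the OLE, 118 to 142 with 48 OLE weeks (SAP section 2) and 166 to 190 with 96 (Protocol 4.1). All three match the stated durations, and none contains a gap.

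**Inputs**
- DBP: 48 to 72 weeks (both documents).
- OLE: 48 weeks (SAP) or 96 weeks (Protocol Edition 6.0).
- Each dose is credited with 28 days, so dosed time for a completer is weeks × 7.
- 5 months is taken as 5 × 365.25/12 = 152.2 days (21.7 weeks).
- Visit 1E gap beyond the credited days: up to 152.2 days.
- Visit 13E gap beyond the credited days: up to 152.2 − 28 = 124.2 days (17.7 weeks).

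**Formula:** overstatement = uncovered gap days / dosed days. The offset of one day either way in the two SAP formulas is ignored; for a 336-day DBP, section 10 gives 337 days and 24.6 gives 335.

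**Whole-study value, completers on Lu AF82422 in both periods**

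| DBP + OLE (weeks) | Dosed days | Visit 1E gap 152.2 d | Visit 13E gap 124.2 d | Both, 276.4 d |
|---|---|---|---|---|
| 48 + 48 | 672 | 22.6% | not possible | not possible |
| 72 + 48 | 840 | 18.1% | not possible | not possible |
| 48 + 96 | 1008 | 15.1% | 12.3% | 27.4% |
| 72 + 96 | 1176 | 12.9% | 10.6% | 23.5% |

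With a 48-week OLE, Visit 13E is the end-of-treatment visit and carries no infusion, so its delay cannot fall between first and last dose.

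**Gaps below the maximum, completers**
- Visit 1E at 20 weeks after the last double-blind dose, when the DBP safety follow-up visit falls due: 20 − 4 = 16 uncovered weeks, giving 16/168 = 9.5% to 16/96 = 16.7%.
- 1 month (30.4 days): 30.4/1176 = 2.6% to 30.4/672 = 4.5%.
- 2 months (60.9 days): 60.9/1176 = 5.2% to 60.9/672 = 9.1%.

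**Patients who stop soon after a maximal gap**
- One OLE dose after the Visit 1E gap: 152.2/532 = 28.6% (72-week DBP) to 152.2/364 = 41.8% (48-week DBP).
- Both gaps, then one dose at Visit 13E: 276.4/868 = 31.8% to 276.4/700 = 39.5%.

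**By period**
- DBP: no excess.
- OLE: none from the Visit 1E gap. A maximal Visit 13E delay gives 124.2/672 = 18.5% for a 96-week completer, or 124.2/364 = 34.1% for a patient who stops after the Visit 13E dose.

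**The case against.** The strongest reply is that exposure is meant to be reported by period. Protocol 17.8, SAP section 5 and the 72-week ceiling on the SAP section 10 categories all point that way, and by period the larger gap adds nothing. This stands as far as it goes. It does not explain why 24.6 defines a whole-study value, what the undefined variables EXP1D to EXP3D hold, or which value is summed into PYE. It also leaves the Visit 13E gap in place.

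A reader might infer that PYE is overstated by 10% to 40% for anyone with a gap. The documents do not support that. PYE is not tied to the whole-study value, the upper end needs a patient who stops soon after a maximal gap, and gaps of 1 or 2 months stay below 10% for completers. A reader might also apply both gaps to a 48 + 48 week patient and obtain 39.5/96 = 41%; the table shows why that schedule cannot occur.

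Further limits stand:
- Visit 1E is intended for the same day or as soon as possible, and a delayed Visit 13E is described as exceptional.
- For patients on placebo in the DBP (20 of 60 planned), exposure to Lu AF82422 starts at Visit 1E, so the first gap does not enter it.
- These intervals are dose-free, not drug-free. With a half-life of about 30 days, the end of a maximal Visit 1E gap is (28 + 152.2)/30 = 6.0 half-lives after the last dose.
- SAP 16.1.5 sets PYE beside patient numbers, percentages and event counts. No rate per patient-year is specified.
- SAP section 10 lists all infusion data, so gaps would remain visible in listings.

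**Conclusion.** The point holds in limited form. The whole-study rule in SAP 24.6 counts permitted dose-free time as exposure. For completers on Lu AF82422 in both periods the excess is at most 13% to 23% from the Visit 1E gap, and at most 23% to 27% with both gaps and a 96-week OLE. Under Edition 6.0, a delayed Visit 13E can inflate even OLE-only exposure, by up to 18.5% for a 96-week completer.

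These figures assume 28 credited days per dose, 5 months of average length, and all 24 open-label doses given despite a delayed Visit 13E. They apply to individual patients with gaps; the effect on total PYE cannot be calculated because the number of such patients is not given. An actual overstatement of reported PYE is therefore possible but not established. Efficacy analyses are unaffected.

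**What to change.** In SAP sections 10 and 24.6:
- Calculate exposure as the sum over doses of min(28 days, days to the next dose), with 28 days for the last dose, for the DBP, the OLE and overall. This also replaces two formulas that differ by 2 days.
- State that PYE uses these sums, and define EXP1D to EXP3D.
- Report first-to-last-dose time only under a separate label, as treatment duration including interruptions.
- If any event rate per patient-year is reported, use observation time matched to the adverse-event period as the denominator. SAP 16.1.4 assigns events before the first open-label dose to the DBP, so capped exposure alone would keep the gap's events and drop its time.
- Reconcile the OLE length, which is 48 weeks in the SAP and 96 in the protocol.

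The cost is one extra derivation rule and a slightly smaller reported PYE. No new data are needed, because dose times are already recorded (Protocol 10.11).

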Appendix II SAS[®] Code

Page 65 of 96

CCI	
CCI	
CCI	

Study 18331A - Statistical Analysis Plan

Page 66 of 96

CCI		
CCI		
CCI		
CCI		
CCI		

Study 18331A - Statistical Analysis Plan

Page 67 of 96

Appendix III 'R' code

Study 18331A – Statistical Analysis Plan

Page 68 of 96

'R' Code

CCI		
		I
1		
CCI		
	-	
CCI		
CCI		

Study 18331A – Statistical Analysis Plan

Page 69 of 96

CCI	
Í.	
-	

Appendix IV Study Flow Chart

Study Flow Chart

Visit Number 1 2 3 4 5 6 7 8 9 10 11 12 13 14 15 16 17 18 19 20 21 22 23 24 25 Week ^d 6 2 0 2 4 6 8 10 12 16 20 24 28 32 36 40 44 48 52 56 60 64 68 72 88 Visit Window ^c (days relation option consist) \pm	Visit Name	Screening	Randomization	Baseline + IMP	Telephone Visit	dWI	Site Visit	IMP	Telephone Visit	dMI	IMP	IMP	IMP	IMP	IMP	IMP	IMP	IMP	IMP/EoT ^a	EoT/Withdrawal ^b	$\mathrm{SFU}^{\mathrm{c}}$					
Weekd6-202468101216202428323640444852566064687288Visit Window ^c (days relative to nominal visit) \pm	Visit Number	1	2	3	4	5	6	7	8	9	10	11	12	13	14	15	16	17	18	19	20	21	22	23	24	25
Visit Windowe (days relative to nominal visit) $\frac{1}{3}$ Week^d	6	-2	0	2	4	6	8	10	12	16	20	24	28	32	36	40	44	48	52	56	60	64	68	72	88	Week ^d	6	-2	0	2	4	6	8	10	12	16	20	24	28	32	36	40	44	48	52	56	60	64	68	72	88
Screening/Randomization Procedures and Assessments Signed informed consent $$ $ $ $ $ $ $ $ $ $ $ $ $ $ $ $ $ $ $ $ $ $ $ $ $ $ $ $ $ $ $ $ $ $ $ $ $ $ $ $ $ $ $ $ $ $ $ $ $ $ $ $ $ $ $ $ $ $ $ $ $ $ $ $ $ $ $ $ $ $ $ $ $ $ $ $ $ $ $ $ $ $ $ $ $ $ $ $ $ $ $ $ $ $ $ $ $ $ $ $ $ $ $ $ $ $ $ $ $ $ $ $ $ $ $ $ $ $ $ $ $ $ $ $ $ $ $ $ $ $ $ $ $ $ $ $ $ $ $ $ $ $ $ $ $ $ $ $ $ $ $ $ $ $ $ $ $ $ $ $ $ $ $ $ $ $ $ $ $ $ $ $ $ $ $ $ $ $ $ $ $ $ $ $ $ $ $ $ $ $ $ $ $ $ $ $ $	Visit Window ^e (days rela- tive to nominal visit)		± 3	± 3	± 3	± 3	± 3	± 3	± 3	± 3	± 3	± 3	± 3	± 3	± 3	± 3	± 3	± 3	± 3	± 3	± 3	± 3	± 3	± 3	± 3	± 7
Signed informed consent \checkmark <th< th="">Screening/Randomization Procedures and Assessments	</th<>	Screening/Randomization Procedures and Assessments																									
Demographics (age, sex, race) $$ MSA diagnostic criteria: $$ Possible or probable, $$ MSA-P or MSA-C $$ MSA History $$ MoCA $$ Relevant medical history $$ (e.g., psychiatric, neurological) $$ Recent and on-going medication $$ Height $$ Blood sampling for pregnancy test $$	Signed informed consent	\checkmark																								
race) Image: Construction of the second system	Demographics (age, sex,	\checkmark																								
MSA diagnostic criteria: $$ Possible or probable, MSA-P or MSA-C MSA History $$ MoCA $$ Relevant medical history $$ (e.g., psychiatric, neurolog-ical) $$ Recent and on-going medi-cation $$ Height $$ Blood sampling for pregnancy test $$	race)																									
Possible or probable, MSA-P or MSA-C MSA History $$ MoCA $$ Relevant medical history $$ (e.g., psychiatric, neurolog- ical) $$ Recent and on-going medi- cation $$ Height $$ Blood sampling for preg- nancy test $$	MSA diagnostic criteria:	\checkmark																								
MISAF of MISAFC $$ MSA History $$ MoCA $$ Relevant medical history $$ (e.g., psychiatric, neurolog- ical) $$ Recent and on-going medi- cation $$ Height $$ Blood sampling for preg- nancy test $$	Possible or probable,																									
MISA History $$ MoCA $$ Relevant medical history $$ (e.g., psychiatric, neurolog- ical) $$ Recent and on-going medi- cation $$ Height $$ Blood sampling for preg- nancy test $$	MSA-F 01 MSA-C																							+		
MOCA $$ Relevant medical history $$ (e.g., psychiatric, neurolog- ical) $$ Recent and on-going medi- cation $$ Height $$ Blood sampling for preg- nancy test $$	M GA	· · · ·																								
Relevant medical history (e.g., psychiatric, neurolog- ical) $$ Recent and on-going medi- cation $$ Height $$ Blood sampling for preg- nancy test $$	MOCA	$\frac{\gamma}{\gamma}$																								
Image: the systematric, incurring a systematric, incurring a systematric, incurring a systematric, incurring a systematric systematris systematric systematric systematric systema	Relevant medical history	γ																								
Recent and on-going medi- cation $$ Height $\sqrt{$ Blood sampling for preg- nancy test $$	ical)																									
cation \checkmark Height \checkmark Blood sampling for pregnancy test \checkmark	Recent and on-going medi-																									
Height $$ Blood sampling for preg- nancy test $$	cation																									
Blood sampling for preg- nancy test $$	Height	\checkmark																								
nancy test	Blood sampling for preg-	\checkmark																								
	nancy test																									
MRI scan for eligibility ^T $$	MRI scan for eligibility ^f	\checkmark																						L		
Inclusion/exclusion criteria $\sqrt{\sqrt{1-1}}$	Inclusion/exclusion criteria	\checkmark	\checkmark																							
Signs and symptoms pre- $\sqrt{\sqrt{\sqrt{\sqrt{\sqrt{\sqrt{\sqrt{\sqrt{\sqrt{\sqrt{\sqrt{\sqrt{\sqrt{\sqrt{\sqrt{\sqrt{\sqrt{\sqrt{$	Signs and symptoms pre-	\checkmark	\checkmark	\checkmark																						
sent at SCR, Randomiza-	sent at SCR, Randomiza-																									
administration: recorded on	administration: recorded on																									
an Adverse Event Form)	an Adverse Event Form)																									
Randomization $$	Randomization		\checkmark																	•••						
Efficacy Assessments	Efficacy Assessments																									
UMSARS $\sqrt{\sqrt{\sqrt{\sqrt{\sqrt{\sqrt{\sqrt{\sqrt{\sqrt{\sqrt{\sqrt{\sqrt{\sqrt{\sqrt{\sqrt{\sqrt{\sqrt{\sqrt{$	UMSARS															\checkmark			\checkmark			\checkmark				
SE-ADL $\sqrt{1}$	SE-ADL																		\checkmark					[]		[
COMPASS Select	COMPASS Select																							[]		[
COMPASS Select Change $\sqrt{\sqrt{\sqrt{\sqrt{\sqrt{\sqrt{\sqrt{\sqrt{\sqrt{\sqrt{\sqrt{\sqrt{\sqrt{\sqrt{\sqrt{\sqrt{\sqrt{\sqrt{$	COMPASS Select Change																							[]		[
$\frac{1}{CGI-S}$	CGI-S																	•						[]		[
$\begin{array}{c c c c c c c c c c c c c c c c c c c $	PGI-S									√			, √					• • • •					••••	r		
$\begin{array}{c c c c c c c c c c c c c c c c c c c $	OGLS	•		$\frac{1}{\sqrt{2}}$						\ \			$\frac{1}{\sqrt{2}}$			$\frac{1}{\sqrt{2}}$			$\frac{1}{\sqrt{2}}$			$\frac{1}{\sqrt{2}}$				

Table 1 Study Procedures and Assessments - Double-blind Treatment Period

Study 18331A – Statistical Analysis Plan

Page 72 of 96
Visit Name	Screening	Randomization	Baseline + IMP	Telephone Visit	IMP	Site Visit	IMP	Telephone Visit	IMP	IMP	IMP	IMP	IMP	IMP	IMP	IMP	IMP	IMP/EoT ^a	EoT/Withdrawal ^b	SFU^c					
Visit Number	1	2	3	4	5	6	7	8	9	10	11	12	13	14	15	16	17	18	19	20	21	22	23	24	25
Week ^d	6	-2	0	2	4	6	8	10	12	16	20	24	28	32	36	40	44	48	52	56	60	64	68	72	88
Visit Window ^e (days rela- tive to nominal visit)		± 3	± 3	± 3	± 3	± 3	± 3	± 3	± 3	± 3	± 3	± 3	± 3	± 3	± 3	± 3	± 3	± 3	± 3	± 3	± 3	± 3	± 3	± 3	± 7
Fall diary, daily recording		\sqrt{g}	\sqrt{h}				\sqrt{g}		\sqrt{h}		\sqrt{g}	\sqrt{h}		\sqrt{g}	\sqrt{h}		\sqrt{g}	\sqrt{h}							
FeetMe® (subset) op- tional ^x		\sqrt{i}	√j				\sqrt{i}		√j		\sqrt{i}	√j		\sqrt{i}	√j		\sqrt{i}	√j							
PAMSys (subset) optional ^x		\sqrt{i}	√j				\sqrt{i}		√j		\sqrt{i}	√j		\sqrt{i}	\sqrt{j}		\sqrt{i}	√j							
MRI scan: vMRI, DTI and ASL measures ^{v,w}			√						\checkmark			\checkmark						\checkmark						√ ^t	
CSF sampling ^k for NfL and t-tau			\checkmark															\checkmark						\sqrt{u}	
Blood sampling for NfL			\checkmark						\checkmark						\checkmark			\checkmark						\checkmark	
Quality of Life Assessment	S																								
EQ-5D-5L			\checkmark															\checkmark						\checkmark	
Pharmacokinetic Assessme	ents																								
Blood sampling for IMP quantification ¹			$\sqrt{1}$		\checkmark	\checkmark	\checkmark		$\sqrt{1}$			\checkmark			$\sqrt{1}$			\checkmark			\checkmark			\checkmark	\checkmark
CSF sampling ^k for IMP quantification			\checkmark															\checkmark						\sqrt{u}	
Target Engagement Assess	mei	nts			_								_						_						
CSF sampling ^k for α-synu- clein and pathological spe- cies of α-synuclein			\checkmark															\checkmark						\sqrt{u}	
Blood sampling for α -synuclein ¹			$\sqrt{1}$		\checkmark	\checkmark	\checkmark		$\sqrt{1}$			\checkmark			$\sqrt{1}$			\checkmark			\checkmark			\checkmark	
Safety Assessments																									
Adverse events						\checkmark		\checkmark						\checkmark		\checkmark				\checkmark					
Follow-up of adverse events on-going at EoT or withdrawal, and new AEs and SAEs																									\checkmark
Blood and urine sampling for clinical safety labora- tory tests	V		\checkmark		\checkmark	\checkmark	\checkmark		\checkmark			V			\checkmark			\checkmark			\checkmark			\checkmark	\checkmark
Blood sampling for ADAs	[\checkmark			\checkmark	\checkmark		\checkmark					••••	\checkmark		[\checkmark			\checkmark	••••		\checkmark	\checkmark
Vital signs ^m						\checkmark			\checkmark		\checkmark			\checkmark		\checkmark	\checkmark			\checkmark			\checkmark		
Weight	\checkmark		\checkmark						\checkmark						\checkmark			\checkmark						\checkmark	
Examinations (physical, neurological) ⁿ	\checkmark		\checkmark		\checkmark	√			\checkmark			\checkmark			\checkmark			\checkmark						\checkmark	
ECG	\checkmark		\checkmark			\checkmark												\checkmark							
MRI scan for safety ^w	[\checkmark						\checkmark			\checkmark						\checkmark						\sqrt{t}	
C-SSRS°	\checkmark	_				\checkmark	\checkmark	-	\checkmark					\checkmark	\checkmark		\checkmark		\checkmark	\checkmark			\checkmark		

Study 18331A – Statistical Analysis Plan

Page 73 of 96

Visit Name	Screening	Randomization	Baseline + IMP	Telephone Visit	IMP	Site Visit	IMP	Telephone Visit	IMP	IMP/EoT ^a	EoT/Withdrawal ^b	SFU^{c}													
Visit Number	1	2	3	4	5	6	7	8	9	10	11	12	13	14	15	16	17	18	19	20	21	22	23	24	25
Week ^d	6	-2	0	2	4	6	8	10	12	16	20	24	28	32	36	40	44	48	52	56	60	64	68	72	88
Visit Window ^e (days rela- tive to nominal visit)		± 3	± 3	± 3	± 3	± 3	± 3	± 3	± 3	± 3	± 3	± 3	± 3	± 3	± 3	± 3	± 3	± 3	± 3	± 3	± 3	± 3	± 3	± 3	± 7
Biobanking																									
Blood sampling for gene expression profiling (RNA) ^p			V									V						V							
Blood sampling for metab- olomics/proteomics (plasma) ^p			V									V						V							
Blood sampling for phar- macogenetics (DNA) (op- tional) ^q			V																						
Blood sampling for ADA	l		\checkmark		\checkmark	\checkmark	\checkmark		\checkmark			\checkmark			\checkmark			\checkmark			\checkmark			\checkmark	\checkmark
CSF sampling ^k																		\checkmark						\sqrt{u}	
Other Study Procedures an	nd A	Asse	ssm	ents	6																				
IMP administration ^m					\checkmark				\checkmark					\checkmark	\checkmark	\checkmark		\checkmark	\checkmark	\checkmark	\checkmark	\checkmark	\checkmark		[
Concomitant medication (prescription and non-pre- scription)	V	V	\checkmark	\checkmark	\checkmark	\checkmark	V	V	V	V	V	V	\checkmark	V	V	\checkmark	V	\checkmark	\checkmark	\checkmark	\checkmark	V	\checkmark	V	V
Pregnancy test, urine dip- stick ^r		\checkmark	\checkmark		√		√		\checkmark	\checkmark	\checkmark	\checkmark	\checkmark	√	√	\checkmark	\checkmark	\checkmark	\checkmark	\checkmark	\checkmark	√	\checkmark	√	V
Exit interview (subset) ^s																									

ADA = Anti-Drug Antibody; AE = adverse event; ASL = arterial spin label; BL = baseline; CGI-S = Clinical Global Impression – Severity of Illness; CSF = cerebrospinal fluid; C-SSRS = Columbia-Suicide Severity Rating Scale; COMPASS = Composite Autonomic System Score; DNA = deoxyribonucleic acid; DTI = diffusion-tensor imaging; ECG = electrocardiogram; EoT = End-of-Treatment; EQ-5D-5L = Euroqol 5 Dimensions-5 Levels; IMP = investigational medicinal product; IRT = Interactive Response Technology; MoCA = Montreal Cognitive Assessment; MSA-C = Multiple System Atrophy with predominant cerebellar features; MSA-P = Multiple System Atrophy with predominant parkinsonism; MRI = magnetic resonance imaging; NfL = Neurofilament Light chain; OGI-S = Observer-rated Global Impression-Severity of Illness; PGI-S = Patient Global Impression-Severity of Illness; SAE = serious adverse event; SE-ADL = Schwab & England Activities of Daily Living; SFU = Safety Follow-up of DBP; SCR = screening; T-tau = total tau; UMSARS = Unified Multiple System Atrophy Rating Scale; vMRI = volumetric magnetic resonance imaging

a. When the last patient randomized reaches Visit 18/Week 48, the remaining patients in the double-blind treatment period will have their next scheduled visit converted to an EoT Visit (assessments as listed for Visit 24, no IMP administration).

b. Patients who withdraw, except for those who withdraw their consent, will be asked to attend a Withdrawal Visit as soon as possible.

c. The Safety Follow-up Visit will take place 20 weeks after last IMP administration. This will apply only to patients who do not enter the OLE or if timing of the safety FU will be before their first visit in the OLE.

Study 18331A - Statistical Analysis Plan

d. All assessments may be completed over a maximum of 2 consecutive days (except for MRI, see footnote w); if so, the first day is considered the "visit" day according to the schedule and at IMP Visits, IMP must be registered in IRT and administered on the second day. The Screening Visit can be performed over 2 days during the first week of the Screening Period.

e. If the date of a visit does not conform to the schedule, subsequent visits should be planned to maintain the visit schedule relative to screening for Visit 2 and Visit 3 and relative to baseline for visits after baseline.

f. MRI scan for eligibility can be performed between Visit 1 and Visit 2. The MRI scan should be uploaded for central reading no later than ten calendar days before the Randomization Visit.

g. Dispense fall diary. This does not apply to a patient who scores 4 on UMSARS Part I item 7 (walking) or if the patient is wheelchair bound for unrelated disorders. This needs to be evaluated at each visit, where the fall diary is dispensed.

h. Return of the fall diary. Patients who withdraw during a period with fall diary entries must return the diary at the Withdrawal Visit.

i. Sensor subset: at the US sites, the patients can participate in an optional objective sensor-based assessments subset. The patients undergoing the additional objective sensor-based assessments must provide specific consent as part of the main *Informed Consent Form*. The patient does not have to consent to both objective sensor-based assessments to participate. The sensor(s) will be applied during the clinic visit. The use of the sensors does not apply to a patient who scores 4 on UMSARS Part I item 7 (walking) or if the patient is wheelchair bound for unrelated disorders. This needs to be evaluated at each visit, where the sensors are dispensed.

j. Return of the sensor(s). Patients who withdraw during a period with objective sensor-based assessments must return the sensor(s) at the Withdrawal Visit.

k. CSF sampling not applicable for patients with contraindications of lumbar puncture, history of severe post-lumbar puncture headache, on-going skin infection at the lumbar puncture injection site or documented history of vertebral deformities, major lumbar back surgery, clinically significant back pain, clinically significant abnormal x-ray, and/or injury that, in the opinion of the investigator, would preclude CSF collection. CSF sampling, when performed at baseline, should be completed prior to IMP administration.

l. Multiple samples to be taken relative to IMP infusion: before infusion (at the same time as sampling for clinical safety laboratory tests), immediately after the end of infusion (EOI), 1 and 2 hours after EOI at baseline, Week 12 and Week 36. At all other visits with blood PK and α -synuclein sampling, samples will be taken before infusion.

m. Blood pressure and pulse will be measured immediately prior to IMP administration and patients will be monitored after IMP administration for immediate drug reactions for a minimum of 2 hours with vital signs taken every 30 minutes (±5 minutes) or until stable, whichever is later.

n. Including recording of use of feeding tube and/or wheelchair.

o. Different versions will be used: 'Baseline/Screening' version at Visit 1 and at Visit 3 and 'Since last visit' version at subsequent visits.

p. Exploratory gene expression profiling (RNA) and metabolomics/proteomics are an integrated part of the study and are covered by the main *Informed Consent Form*.

q. Sampling for pharmacogenetics is optional and a separate signed *Informed Consent Form* must be in place to cover this analysis.

r. If positive, confirm with serum pregnancy test.

s. Exit Interview subset: at the US sites, the patients and caregivers will undergo the Exit interviews via telephone or web conferencing platform (e.g., Microsoft Teams). The Exit interview will be conducted within 3 weeks after the EoT Visit or within 3 weeks after the Withdrawal Visit for patients who reach a 48-week treatment period but withdraw prior to the EoT Visit. Study Experience Interview subset: at US sites, a subset of patients and caregivers may be contacted to participate in a Study Experience interview by telephone or web conferencing platform (e.g., Microsoft Teams). The Study Experience interview will be conducted within 6 weeks after the completed Exit interview for patients who consent.

t. MRI scanning only to be performed as EoT/withdrawal procedure if not performed within the last 8 weeks.

u. CSF sampling only to be performed as withdrawal procedure in case of withdrawal prior to Visit 18/Week 48 and for patients with EoT at Visit 18/Week 48. Patients with EoT after Visit 18/Week 48 will not undergo CSF sampling as part of the EoT procedures.

v. DTI and ASL measures where available. If Visit 3 MRI scanning is performed without DTI and/or ASL sequences and these sequences are implemented in the scanner at a later stage, DTI and ASL should not be performed at subsequent visits with MRI measurements.

w. MRI scan can be performed any day within the Visit Window, except for Visit 3 where it must be performed before IMP administration. Date of MRI scan will not define Day 1 or Day 2 of a visit and will not be regarded as a separate visit.

